I agree to ensure that the confidential information contained in this document will not be used for any other purpose other than the evaluation or conduct of the clinical investigation without the prior written consent of the Sponsor.

I also confirm that I will make the findings of the study publically available through publication or other dissemination tools without any unnecessary delay and that an honest accurate and transparent account of the study will be given; and that any discrepancies from the study as planned in this protocol will be explained.

For and on behalf of the Study Sponsor:

Signature:

Date:...../...../.....

Name:

Position:

Chief Investigator:

Signature:

Date:15/02/16

Name: [name]

3. Study Summary

Short Title	The Haus Study – Phase II
Methodology	This protocol describes a prospective, mixed methods, non-randomised study to determine the feasibility and acceptability of a provider initiated, HIV self-sampling kit (SSK) distribution intervention targeted at Black Africans. The study evaluates the effectiveness of self-sampling for HIV in increasing the uptake of HIV testing by Black Africans as well as the cost effectiveness of distributing the SSK among Black Africans over other screening methods. Feasibility, acceptability and intervention fidelity will also be assessed through a process evaluation.
Research Settings	GP practices and HIV Community Based Organisations (CBO)
Research Sites	GP Practices in South London and Greater Glasgow. HIV Community based organisations in both cities.
Aims and Objectives	Overall the study aims to develop an HIV SSK intervention to increase the provision and uptake of HIV testing among Black African communities using existing community and healthcare provision. The aim of Phase II is to evaluate an HIV self-sampling kit distribution intervention targeted at Black Africans. Phase II specifically assesses the feasibility and acceptability of GP practices and community based organisations for targeted HIV SSK distribution. Phase II will inform optimal intervention design for development of a protocol for a future substantive phase III evaluation where this is deemed feasible.
2	1580 kits will be distributed to 1580 participants. 600 kits will be distributed per distributor type in London (600 by GP practice nurses and 600 by community workers) and 380 distributed in Glasgow (via primary care only).
Main inclusion criteria	Black African people without diagnosed HIV, 18 years of age or older, who access the selected GP practices and services provided by Community organisations that already undertake HIV prevention interventions. GP practices in London and Greater Glasgow that have significant numbers of Black Africans registered with them and have not been recently involved in large scale HIV testing initiatives. Community based organisations in London that currently provide HIV prevention interventions for African people.
Main Outcomes	The primary outcome is HIV SSK return rate.
Data Analysis	Quantitative analysis to quantify HIV SSK return rate and other secondary quantitative outcomes. Framework Analysis of all qualitative data collected.
Proposed Start Date	4 th January 2016 (Phase II)
Proposed End Date	30 th September 2016

4. Introduction

4.1 Background and Rationale

Despite progress in treatment and care, Black Africans in the UK continue to present with advanced disease to HIV services. While barriers such as stigma and fear persist, research and experience suggests that when provided the opportunity, many Africans test for HIV (1, 2). In the UK, access to HIV testing is predominantly through sexual health clinics, a service not regularly accessed by African communities. Although primary care services are utilised by this population, these opportunities for earlier HIV diagnosis are often missed (3). African men in particular have high rates of undiagnosed infection and late presentation (1), partly because they have less contact with health services than women. Innovative methods to increase the uptake and opportunities for HIV testing in this population are required.

Self-collected specimens can be used reliably to test for HIV. Self-sampling kits (SSK), accessed via clinical settings and the internet have been shown to be an acceptable and feasible alternative to clinic attendance for HIV testing, and may increase testing among hard-to-reach men who have sex with men (4). Research among young men in the UK also demonstrated acceptability to SSK for HIV testing, with traditional healthcare settings being the preferred venue for accessing kits (5). No study, however, provides insights into preferences by ethnicity, or among women and older men. A survey using oral swabs for anonymous HIV testing among African men and women, in community settings detected high rates of undiagnosed HIV (6), indicating that if testing were offered in these settings, it could lead to new diagnoses and facilitate timely linkage to care. Currently, there are no data on the acceptability or feasibility of using SSK to increase the uptake of named HIV testing among black Africans in the UK. It is important to establish how best to embed SSK within existing services, to ensure acceptability to both provider and client, and to optimise uptake for cost effectiveness. For example linking the kits to existing health promotion and NHS screening opportunities, may facilitate uptake of HIV testing. In a recent cross-sectional study undertaken among Black Africans in England, nearly one third of participants without diagnosed HIV said that they would prefer to have a future HIV test at their GP surgery (7). It is also vital to establish acceptable pathways to confirmatory testing and specialist HIV care. Africans in the UK do not represent a homogenous group and it is important to place efforts to increase HIV testing within the wider social, political and cultural context (8, 9). In advance of undertaking a UK wide study, it is important to understand how distinct health care systems and differences in HIV and community services, as well as differences in local populations and proportions of Africans and HIV prevalence, may impact on the acceptability, feasibility, and cost effectiveness of the interventions. We aim to

improve the provision, acceptability and uptake of HIV testing by developing SSK distribution interventions within GP settings and community based organisations.

Throughout this proposal the term 'Black African' includes anyone who identifies themselves as Black African, whether they are migrants from Africa, African descendants or African nationals. Black African communities encompass diverse population groups including people who may be heterosexual, bisexual or homosexual.

We have named our study the 'Haus study' after the West African pidgin term for "home".

4.2 Phase 1 findings

This protocol and the intervention that will be described later have been informed by Phase 1 of this research. This involved a systematic review and extensive qualitative work conducted between June 2014 and December 2014. The first phase of the Haus Study aimed to develop acceptable SSK distribution pathways in community-based health and HIV prevention services already accessed by Black African people. The full findings are to be published in open access peer-reviewed journals but a summary of the key findings will be presented in section 4.2.2 below. The objectives of Phase 1 were to:

- Clarify barriers and facilitators to provision, access and use of HIV SSK by Black African people, in primary care, pharmacies and community outreach.
- Determine appropriate SSK-based intervention model(s) for different settings.
- Develop intervention manuals to enable intervention delivery in different settings.
- Build sustainable relationships with community service providers willing to distribute and evaluate SSKs as an add-on to existing services.

4.2.1 Qualitative work

We conducted twelve focus group discussions (FGDs) in London and in Glasgow. Six FGDs were conducted with Black Africans, three in Glasgow, and three in London.. We recruited purposively to ensure diversity of gender, age, region of origin and HIV testing experience. Our recruitment strategy enabled us to have the following FGDs:

- 1 group of people with diagnosed HIV (Glasgow)
- 1 men only group (London)
- 1 young person's group (less than 30 years old) (London)
- 3 mixed (gender, age and HIV testing experience) groups (London and Glasgow)

In total there were 47 lay participants (men n=23 and women n=24), including 18 participants who had never previously tested for HIV. In the group discussions we examined views towards SSK, rationales for selecting potential community settings, and key features of implementation.

We also conducted six FGDs with professionals who provide services to Black Africans (n=53).

Participants included:

- practice nurses;
- health care assistants;
- GPs;
- Pharmacists and pharmacy assistants
- Those working and volunteering in African community organisations
- African faith leaders.

The focus groups examined attitudes towards SSK, rationales for selecting potential settings, and key features of implementation. These same issues were explored in nine additional qualitative interviews with HIV clinicians and service commissioners in London and Glasgow.

In summary the key findings from the qualitative work in Phase 1 are:

1. Self-sampling was viewed as acceptable, convenient, anonymous, discrete, private and enabling patient autonomy. However there were some concerns about isolation, lack of counselling, security of samples in transit, accuracy and reliability of the result from a self-sampling kit.
2. It is a viable option to distribute the SSKs through GP practices and community based organisations (CBOs).
3. To enable the research team to track distribution and return of self-sampling kits, it was recognised that provider controlled distribution was required and was considered acceptable.
4. It appears that opportunistic offer of the kit by the staff nurse in the GP practice would be the most appropriate in this setting as it strikes a balance between privacy, confidentiality and busy surgery appointment schedules.
5. Staff in CBOs are regarded as having the requisite HIV skills, cultural competence and infrastructure which makes them well-placed to distribute SSKs.

6. There were significant concerns about the TINY¹ kit including:
 - The presumed large volume of blood required to process the sample.
 - Many people having a fear of needles.
 - Presumed difficulty in using the kit
 - Fear of contamination of the vial.
 - Fears about contaminating others.
7. For those familiar with SSKs, the oral swab was identified as an easier alternative to the use of the TINY kit. There were mixed views about the Dried Blood Spot kit as an alternative to the TINY kit.
8. Provider initiated targeting for offering HIV testing was understood as more likely to succeed than a patient initiated approach. However, consideration of the actual locations in which targeting conversations could take place was perceived as a vital component of the intervention.
9. It was regarded as very important that targeting conversations were initiated sensitively and the content of such conversations were considered in detail in order to avoid perceptions of racism.
10. Provider-initiated targeting which used appearance alone was generally understood as unacceptable. Targeting which addressed more detailed issues such as country of origin or national identity were understood as more acceptable however, they could still be understood as problematic.
11. Tailoring the intervention for individual circumstances was understood as reducing the key barriers of perceived racism and discrimination.
12. For service delivery, it would be better if personal details were not collected at the point of kit collection from a service provider however it was acceptable to have these collected for the purpose of a study and by a trusted professional.
13. It is acceptable for participants to receive a non-reactive result via text message.
14. It is acceptable for the standard NHS clinical governance mechanisms for HIV result management to be used for the study.

¹ TINY kit requires collection of a few drops of blood (obtained by pricking a finger with the supplied lancet) in a small collection vial. The test enables the specimen to be transported to a lab, by post, in a vial that contains preservatives, which stabilize the sample for up to 21 days if temperatures are between 4° C and 37° C.

4.2.2 Systematic Review

As part of the preparatory phase, we also conducted a systematic review of literature, legal, policy and regulatory publications on HIV self-sampling. A full paper on the systematic review is due to be submitted for publication in August 2015. In brief, 15 studies met the inclusion criteria for the systematic review. Below we summarise key findings which were important for informing the development of the intervention:

1. It is feasible and acceptable to use home self-collection kits for HIV testing. In the studies reviewed SSKs were seen as convenient; time saving; private (10, 11, 12, 13, 14, 15, 16).
2. Collection of kits from medical settings such as STI clinics, surgeries, and pharmacies is acceptable (10, 16).
3. SSKs can also be distributed in community settings and outreach services (11, 16).
4. The oral swab is preferred to kits that used blood specimens (15, 19).
5. Barriers to use of SSK include:
 - Concerns about accuracy of the test result (16, 17).
 - Embarrassment about being seen purchasing a kit or asking for it (11, 18).
 - Lack of counselling opportunity (16, 19)

We have developed the intervention and protocol to reflect the current body of knowledge with regards to the use of HIV self-sampling kits.

4.2.3 Professional Guidance relevant to development of HIV testing services

Throughout the design of the intervention and this protocol, we have had discussions with experienced senior NHS HIV service managers; community workers, practice nurses, GPs, HIV commissioners as well as managers from the HIV voluntary sector to assess the planned intervention and research. We have also drawn upon the expertise of the research team and members of the study steering committee to enable us to adopt validated components of the intervention.

The qualitative work, the systematic review and professional guidance suggested user and provider preference for use of a saliva based SSK. The OraSure kit is a commercially available oral fluid collection kit and it is CE marked, but there are no CE marked saliva based HIV assays currently available in the UK. The GENSCREEN™ ULTRA assay is used for the detection of HIV p24 antigen and antibodies to HIV-1 (Groups M and O) and HIV-2, thus when used with plasma and serum it is considered a fourth-generation assay, and has a sensitivity of 100% (93.2% in the seroconversion scenario), so it is a reliable indicator when a result is negative, especially as

incident infection is likely to be low in this population. The assay's specificity has been assessed as 98.72% -99.95% depending on the study population. When used with saliva it is regarded as a third generation assay as it is unable to reliably detect p24 antigen. This means it is less sensitive to very recently acquired infection and is used to detect HIV that was caught more than 14 weeks ago. Despite this, commercial and NHS services throughout the UK have and continue to use the assay with saliva because of the reasons detailed above. In these instances the healthcare establishment takes on liability with reference to the device being used 'off-label' (20). To do this the clinical service usually performs an in house performance evaluation.

Despite the absence of a CE marked assay for saliva HIV testing, on 22nd May 2015 there was a call for expressions of interest in a national self-sampling tender from Public Health England. The call specifically included online distribution of a choice of saliva or blood-based self-sampling for HIV. Formal invitations to tender were issued on 28th July which again included preference for inclusion of a saliva-based option however on the 18th August some clarification on the national tender process were issued. These included the following statement.

“UK national standards (BHIVA 2008) set 4th Generation HIV as their standard. See <http://www.bhiva.org/documents/guidelines/testing/glineshivtest08.pdf>

The commissioning parties entering into this wish to adhere to this standard.

The recommended first-line assay is one which tests for HIV antibody AND p24 antigen simultaneously. These are termed fourth generation assays, and have the advantage of reducing the time between infection and testing HIV positive to one month which is one to two weeks earlier than with sensitive third generation (antibody only detection) assays.

In any event CE marked methods are required in the delivery of this service. Whilst this may restrict the range of home sampling methods that can be used during the initial period of delivery, it gives the provider opportunities to offer other methods, during the life of the contract, as other CE marked products become available.

There is no preferred test kit supplier or manufacturer.”

Thus despite the Orasure SSK being preferred by both service providers and users, University College London Hospitals NHS Foundation Trust (UCLH) and the processing laboratory (The Doctors Laboratory) felt unable to offer a saliva based SSK option and advised we use the CE approved, fourth generation TINY vial. The full intervention is described in section 6.4. In brief, the intervention involves using a designed script to opportunistically offer an HIV SSK to Black African service users during routine engagement with primary care and with services provided by community based organisations. The intervention will be provided by two types of distributors:

- **GP Practice:** Practice Nurses will offer the intervention.

- **Community Based Organisation:** Community workers will offer the intervention during routine outreach services.

Phase 2 will determine the feasibility and acceptability of this provider initiated, HIV self-sampling kit distribution intervention targeted at Black African people.

4.3 Potential Benefits

At an individual level, the potential benefits of the Haus study centre on increasing accessible HIV testing options for Black African people. The benefits of HIV testing are well documented in the literature (22, 23). These include reduction in HIV related morbidity, mortality and preventing onward HIV transmissions (22, 23). Early diagnosis enables patients to benefit from antiretroviral therapy more than those who are diagnosed late (22, 23).

At a public health level, the major advantage would be to expand access to HIV testing to a population who are at a considerably higher risk of HIV infection in the UK and who are more likely to be diagnosed with advanced HIV disease than their non-African counterparts (1). This would have the advantage of increasing the proportion of Black African people who are diagnosed early and receiving HIV treatment. From an economic perspective, targeted interventions mean HIV testing resources can be targeted at populations with the greatest need. If successful, such an intervention could reduce transmission and enhance timely identification of HIV. This impacts individuals and populations by optimising health outcomes and reducing onward transmission rates. There are also economic benefits to diagnosing HIV as soon as possible after infection (22, 23).

4.4 Risks from participating in the study

Our study does not present any elevated risks over the usual risk associated with HIV testing in standard care. It is possible that some patients may find the process of HIV testing distressing; our participant information sheet includes details of where participants can access further information and support. Participants will also have the option to ask the kit distributor if they have further questions about HIV or the SSK. Participants with a reactive result will be supported by experienced NHS staff, who are used to giving these results over the phone and supporting patients with linkage into care and support (see section 6.10 which has further details on results management). It is also possible that some people may object to and become upset at being targeted for the intervention because of their ethnicity (24). All recruiters will be provided training to ensure they are able to explain why Black African communities are being targeted and to reassure prospective participants that the intervention is intended as a health

opportunity for their community rather than a stigmatising activity. The contact details of the project manager and chief investigator are available on the patient information sheet should participants have any questions about the study.

5. Objectives and outcome measures

Hypothesis: Embedding self-sampling kits (SSKs) for HIV testing in existing services is an acceptable and feasible means to increase the provision and uptake of HIV testing among Black Africans residing in the UK.

5.1 Overall aims of phase 2

To assess feasibility, appropriateness of settings and optimal intervention design for future phase III evaluation.

5.2 Primary Objectives of Phase 2

To determine the acceptability and feasibility of a provider-initiated, HIV self-sampling kit distribution intervention targeted at Black African people in GP settings and community based HIV prevention organisations.

5.3 Secondary objectives of phase 2:

1. Determine appropriate SSK-based intervention models for GP settings and community based organisations.
2. Establish acceptability of interventions for providers and users.
3. Evaluate the effectiveness of self-sampling for HIV in increasing the uptake of HIV testing by Black African people.
4. Determine the cost effectiveness of distributing the SSKs among Black African people over other screening methods.
5. Build sustainable relationships with community service providers willing to distribute and evaluate SSKs as an add-on to existing services.
6. Monitor ability to trace participants with reactive results, confirmatory testing and linkage into specialist care.
7. Determine sample size parameters and control population for a phase III trial offering HIV SSK.
8. Determine the cost per person kit distributed and cost per HIV diagnosis per setting.

9. Assess the feasibility of collecting data for a lifetime cost-effectiveness model alongside a Phase III trial.
10. Assess feasibility, and if appropriate the optimal trial design for future phase III evaluation.

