5.5 Secondary Outcome Measure

1. Point of delivery outcomes:
 - Acceptability of targeted HIV SSK distribution, including rationales for accepting or refusing the offer of an SSK
 - Acceptability and feasibility of targeted SSK distribution among specified service providers, including utility of protocols for SSK targeting, offers and intervention uptake.
2. Data collection outcomes:
 - Demonstration that intervention models and service provider training and support incorporates sufficient capacity to successfully record the numbers of: people offered SSK, accepting SSK, and returning SSK
 - Feasibility of collecting correct contact details enabling follow-up, reminders and communication of results
3. Pathway to care outcome measures:
 - Proportion of those whose samples are reactive who: a) are informed of results in person and b) who attend for confirmatory testing at an NHS setting of their choice
4. Overarching outcome measures:
 - Cost per person kit distributed and cost per HIV diagnosis per setting
 - Attrition rates and loss to follow up
 - Confirmatory testing, proportion of those receiving an HIV positive diagnoses, and clinical stage at diagnosis
 - Feasibility and sensitivity of outcome measures (testing, behavioural and economic) for a definitive trial.

6. Study Design

This is a prospective, mixed-methods, non-randomised study. The study evaluates the effectiveness of self-sampling for HIV as well as the cost effectiveness of distributing the SSK through GP settings and Community based organisations. Feasibility and acceptability will also be assessed through a process evaluation. Please see the fieldwork schematic diagram in section 6.1 for further information.

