7.2.3 Economic Evaluation

A positive diagnosis of HIV has significant cost and quality of life implications, the measurement of which are beyond the remit of this project, but are a key consideration in assessing the cost-effectiveness of an intervention to distribute SSK among Black African people compared to current screening methods. We will assess the feasibility of collecting information to inform key parameters for a life decision analytical model of SSK as a screening method for Black African populations by setting. These variables will include (i) the cost of the test including postage and packaging and any costs to services of giving out the test including training (ii) return rates (iii) cost of processing returned tests (iv) proportion of reactive and subsequently positive tests of those returned (v) clinical stage at diagnosis (vi) cost of confirmatory and additional testing on all reactive results and insufficient samples respectively. From this information a cost per test returned and a cost per positive and negative diagnosis can be calculated.

Models of HIV screening and the lifetime costs and outcomes associated with different screening methods are currently in development. We will assess the possibility of using previously developed decision analytical models for cost-effectiveness analysis that can report a life time cost per quality adjusted life year (QALY) gained of SSK sampling in different settings compared to current practice in Black Africans in the UK. In addition to the information mentioned above, prevalence and incidence of disease in this group are also likely to be important parameters for the model, along with other characteristics that differ to the UK general population. If suitable decision analytical models do not already exist one would need to be developed as part of a full trial.

We will conduct a budget impact analysis to determine the cost to commissioners of screening for HIV in Black Africans across current settings based on the number of Black African people in their local community; test uptake rates; cost per test and cost per positive diagnosis as calculated above, by setting; and cost of HIV treatment dependent on stage of disease.

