14.2 Outputs

If our findings demonstrate that a Phase III trial is feasible then our primary output will be an intervention manual to enable replication in a subsequent UK wide Phase III RCT. The manual will include parameter estimates for the required sample size and a cost effectiveness analysis. It will provide guidance as to appropriate trial design for a given setting. The manual will enable a subsequent trial team to undertake the necessary processes for successful trial implementation.

We will compile a study report that summarises the key findings, and clearly outlines the methods utilised to design and deliver the intervention in each setting, for each population, and the rationales for the selection of study sites and sub-populations. The report will describe the processes of HIV SSK distribution, staff training, sample collection, communication of results and confirmatory testing.

Given that this is a feasibility phase II study, the routes to direct impact will follow through a subsequent trial and its outcomes. Nonetheless, there is little current evidence regarding the uptake of new HIV testing technologies among Black African people in the UK. This project will

provide evidence for NHS commissioners and service providers regarding the acceptability and feasibility of outcome evaluation and a budget impact analysis of screening for HIV across different settings. By examining the feasibility and acceptability within GP surgeries and community based organisations, we also provide evidence for alternate models for reaching Africans.

Trials and interventions to broaden access to HIV SSK are starting to emerge, but the proposed research offers an opportunity to extend the knowledge base. Additionally, we acknowledge that a range of statutory and commercial programmes seeking to expand distribution of SSKs to both narrowly and broadly targeted populations are already in place, and will continue to emerge throughout the course of the proposed research. The technology is already licensed and available (www.drthom.com, www.ruclear.co.uk).

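### Secondary objectives 3 and 4 are comparative aims that a design giving every participant a kit cannot answer

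*Protocol*

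**What the plan says.** Section 5.3 lists ten secondary objectives. The third is to "Evaluate the effectiveness of self-sampling for HIV in increasing the uptake of HIV testing by Black African people". The fourth is to "Determine the cost effectiveness of distributing the SSKs among Black African people over other screening methods". The Study Summary (section 3) carries the same two aims and presents the first as what the study does: "The study evaluates the effectiveness of self-sampling for HIV in increasing the uptake of HIV testing by Black Africans". Section 6.4 and section 1.2 of the intervention manual (Appendix 6) add that the purpose is to find out whether distributing kits raises testing in African communities.

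The design is described in section 6: "This is a prospective, mixed-methods, non-randomised study". The Study Summary gives its size: "1580 kits will be distributed to 1580 participants". These are 600 from London practice nurses, 600 from London community workers and 380 from Glasgow primary care. The primary outcome (section 5.4) is the kit return rate. Objective 7 in section 5.3 places the choice of a control population among the things to be settled for phase III.

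On the economics, section 7.2.3 says of the cost and quality-of-life implications of a positive diagnosis: "the measurement of which are beyond the remit of this project". It then undertakes to assess whether model parameters can be collected and whether an existing decision model could be used against current practice. If no suitable model exists, it leaves building one to a full trial. Section 6 nevertheless states: "The study evaluates the effectiveness of self-sampling for HIV as well as the cost effectiveness of distributing the SSK", and section 14.2 says: "The manual will include parameter estimates for the required sample size and a cost effectiveness analysis".

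**The concern.** To say that testing was increased is to say that it is higher than it would otherwise have been. To say that one method is cost-effective over others requires costs and outcomes for those others. The design follows only people who accepted a kit, and its outcome, return of that kit, has no meaning for anyone without one. Some of these people would have tested by another route. The protocol itself expects this: the refusal codes in Appendix 3 include having tested recently and preferring to test elsewhere.

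At stake is what the final report may conclude on two stated objectives. Sections 14.1 and 14.2 name commissioners and service providers among the users, some of whom may act before a randomised trial reports. A return rate reported under a heading about increased uptake could be taken for an effect size.

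**Working it through.** **Inputs.** Kits per group: 600, 600 and 380 (Study Summary; section 7.1). Assumed return rate 50%, stated precision ±4.0% and ±5.0% (section 7.1). The confidence level is not stated; 95% is assumed here.

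**Step 1: the plan's own figure.** Half-width = 1.96 × √(p(1 − p)/n) at p = 0.5.

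- n = 600: 1.96 × √(0.25/600) = 0.0400, or ±4.00 points.
- n = 380: 1.96 × √(0.25/380) = 0.0503, or ±5.03 points.
- Inverted, n = 1.96² × 0.25/d² gives 601 for d = 0.04 and 385 for d = 0.05.
- Total: 600 + 600 + 380 = 1580.

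The stated precision reproduces to rounding. It is the precision of a return rate within a setting. Section 7.1 gives no effect size and no comparison, and uses the word power to mean interval width.

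**Step 2: what the groups can contrast.** London GP, London community and Glasgow GP differ by distribution route or city. All three receive kits, so they can be compared with one another but not with no kit or with another screening method. The site characteristics in section 6.2 record whether new patient checks include HIV testing, but no testing rate and no earlier period.

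**Step 3: why the return rate does not give the increase.** Let c be the share of kit-takers who would have tested anyway over the same period. If those who do not return a kit do not test elsewhere, the change in testing is 50% − c. The protocol gives no value for c, so the range below is an assumption for illustration only.

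| c | Change in testing (points) |
|---|---|
| 10% | +40 |
| 20% | +30 |
| 30% | +20 |
| 40% | +10 |
| 50% | 0 |
| 60% | −10 |

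Every row is compatible with the same observed 50%. Any testing elsewhere by non-returners would raise these figures, and the quantitative follow-up in section 6.8.1 does not measure that either.

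**Step 4: the data that come closest.**

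- Baseline question 1 (Appendix 4) asks time since last HIV test, but only of people who enrolled, and no before-after analysis is described.
- Acceptability question 4 (Appendix 5) asks whether the offer helped the decision to test, but reaches only those who send the questionnaire back with the sample.
- The topic guide (Appendix 12, question 1.1) asks about earlier testing or thoughts of it, in about 30 interviews.

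These give self-reported context. None estimates c.

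**Step 5: objective 4 beside section 7.2.3.** The six listed inputs are the cost of the test and of giving it out, return rates, processing cost, proportions reactive and positive, stage at diagnosis, and cost of further testing. They describe the kit pathway. They yield average costs per test returned and per diagnosis. No cost or outcome of an alternative is listed for collection, and the comparative model is only explored. The budget impact analysis gives commissioners' outlay, not an incremental ratio. Objectives 8 and 9 in section 5.3 already state what this section can deliver.

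**The case against.** The strongest defence is that this is a feasibility study and mostly says so. The overall aim, primary objective, primary outcome and sample size concern feasibility, acceptability and return. Section 7.2.1 is descriptive and directed at a definitive trial, and objective 7 shows the authors knew that this study has no control. All of that stands. It limits the weight of the point but does not make objectives 3 and 4 answerable as worded. An analysis plan not shown here could add detail, but not a comparator that the design does not collect.

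Some stronger readings are tempting, and the documents do not support them.

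- *The remit sentence defeats both objectives.* It concerns the cost and quality-of-life consequences of a diagnosis, so it bears on objective 4 only. Objective 3 fails for want of a comparator.
- *Relative cost effectiveness is undefined.* A decision model can take comparator inputs from outside the study, and section 7.2.3 leaves that possibility open. It does not commit to it.
- *Sections 6 and 14.2 flatly contradict section 7.2.3.* Neither names a competing screening method. Section 6 refers to distribution through the two settings, the manual in section 14.2 depends on phase III being judged feasible, and cost per diagnosis can be read as cost effectiveness in natural units. They need aligning but are weaker evidence.
- *The study has nothing on earlier testing.* Step 4 shows that it has something, though not a counterfactual.

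**Conclusion.** The point holds for secondary objectives 3 and 4 and the matching text in the Study Summary. Both claim a comparison that the design does not contain. The size of the gap cannot be estimated from the protocol. The +40 to −10 point spread rests on an assumed c of 10% to 60% and on no testing elsewhere by non-returners, and it shows only that the return rate does not determine the increase.

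A reader might infer that the report is bound to announce an increase in uptake, or that the main result is compromised. The protocol supports neither: the planned analysis is descriptive, and the return rate and its precision stand as stated. This is a correction to the wording of two of ten secondary objectives, worth making before results are reported.

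**What to change.** 1. Restate objective 3, and the matching sentence in the Study Summary, as describing uptake of the offer, the sample return rate, and the share of returners who had never tested or not tested recently. The screening log, the laboratory returns and baseline question 1, linked by kit number, already supply these.
2. Change the purpose statements in section 6.4 and section 1.2 of the intervention manual in the same way, so that they no longer promise to show whether testing rises.
3. Restate objective 4, and its counterpart in the Study Summary, as cost per kit distributed, per test returned and per diagnosis by setting, together with the feasibility of populating a cost-effectiveness model against current practice.
4. Align the cost-effectiveness wording in sections 6 and 14.2 with section 7.2.3.

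The cost is an amendment to wording. The primary objective, primary outcome, sample size and data collection stay as they are. The only loss is that the two secondary claims become more modest.
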